11.1.3 Assessment of Causality

The relationship of each adverse event to the trial intervention must be determined by a suitably qualified individual according to the following definitions:

- Related: The adverse event follows a reasonable temporal sequence from the trial investigational product. It cannot reasonably be attributed to any other cause.
- Not Related: The adverse event is probably produced by the participant's clinical state or by other modes of therapy administered to the participant.

Due to the low-risk nature of the device the assessment of causality will be deemed by the Principal or Chief Investigator as suitably qualified healthcare professionals.

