11 ADVERSE EVENT REPORTING

11.1 Safety Reporting

11.1.1 Adverse Event Definitions

Adverse EventAn event in which care resulted in an undesirable clinical outcome – an outcome not(AE)caused by underlying disease – that prolonged hospital care, caused permanent

| | harm or requires lifesaving intervention or contributed to death. |
|--|---|
| Adverse Reaction (AR) | An untoward and unintended response resulting from an intervention related to the use of an investigational product. |
| Serious Adverse Event (SAE) | A serious adverse event is any untoward medical occurrence that: results in death is life-threatening requires inpatient hospitalisation or prolongation of existing hospitalisation results in persistent or significant disability/incapacity Other 'important medical events' may also be considered a serious adverse event when, based upon appropriate medical judgement, the event may jeopardise the participant and may require medical or surgical intervention to prevent one of the outcomes listed above. NOTE: The term "life-threatening" in the definition of "serious" refers to an event in which the participant was at risk of death at the time of the event; it does not refer to an event which hypothetically might have caused death if it were more severe. |
| Serious Adverse Reaction (SAR) | An adverse event that is both serious and, in the opinion of the reporting Investigator, believed with reasonable probability to be due to one of the trial methodologies or treatments, based on the information provided. |
| Suspected Unexpected Serious Adverse Reaction (SUSAR) | Any events suspected to be caused by the investigational product, but which are not consistent with information about the investigational product. |

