11.1.4 Procedure for Reporting Adverse Events

All AEs occurring during the safety window for the trial as defined above that are observed by the Investigator or reported by the participant, will be recorded during visits on the participants electronic

health record as source data and recorded on the CRF for the purposes of the study, whether or not attributed to the Salurate device.

The following information will be recorded on the CRF: description, date of onset and end date, severity, assessment of relatedness to investigational product, other suspect drug or device and action taken. Follow-up information should be provided as necessary until the AE has resolved or stabilised.

The severity of events will be assessed on the following scale: 1 = mild, 2 = moderate, 3 = severe.

Non-serious AEs considered related to the study intervention as judged by the Principal or Chief Investigator or the Sponsor will be followed up until resolution, or the event is considered stable.

It will be left to the Investigator's clinical judgment to decide whether an AE is of sufficient severity to require the participant's removal from treatment. A participant may also voluntarily withdraw from treatment due to what they perceive as an intolerable AE. If either of these occurs, the participant will be thanked for their involvement and followed up by telephone until the AE is resolved or considered stable. All withdrawals must be recorded using document *HR-P-62 - Early Withdrawal Form*.

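### The two causality classes in 11.1.3 leave a gap and use a stricter test than the SAR and SUSAR definitions in 11.1.1

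*Protocol*

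**What the plan says.** Protocol 11.1.3 makes the classification compulsory for every event: "The relationship of each adverse event to the trial intervention must be determined by a suitably qualified individual according to the following definitions". Two definitions follow.

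- **Related** has two conditions. The first is timing: "The adverse event follows a reasonable temporal sequence from the trial investigational product". The second is exclusion of alternatives: "It cannot reasonably be attributed to any other cause".
- **Not Related** applies when "The adverse event is probably produced by" the woman's clinical state or another treatment.

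There is no intermediate level. Because the device is low risk, the judgement is left to the Principal or Chief Investigator.

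Protocol 11.1.1 uses other tests. A SAR is a serious event that the reporting investigator finds "believed with reasonable probability to be due to one of the trial methodologies or treatments". A SUSAR covers "Any events suspected to be caused by the investigational product" that do not match the information held on the product.

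Relatedness to the product is one of the items recorded on the CRF under 11.1.4. The same section contains one rule that depends on it: "Non-serious AEs considered related to the study intervention as judged by the Principal or Chief Investigator", or by the Sponsor, are followed until they resolve or are stable.

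**The concern.** A causality scale should give each event exactly one class, and that class should agree with the definitions that separate a SAR or SUSAR from any other SAE. Here the two classes are not complements, and 'Related' is set at a higher level of certainty than either definition in 11.1.1. An investigator who thinks that the device may have caused an event, but who sees another reasonable explanation, has no class to enter and no rule on which test prevails. Two investigators could enter the same event differently and both be within the protocol.

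The safety listing would then carry relatedness entries of uncertain meaning, and a serious event could be judged against the stricter test and not be recognised as a SAR or SUSAR.

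**Working it through.** No arithmetic applies, because the protocol gives no figure on this point. The check sets the definitions side by side and then asks which procedures use the result.

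**Step 1. Do the classes cover every event?** Take an event in plausible time sequence with sampling and vary the strength of the alternative cause.

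| Alternative cause (own condition or other treatment) | Class under 11.1.3 | If serious: SAR or SUSAR under 11.1.1 |
|---|---|---|
| Not reasonable | Related | Can be met; consistent |
| Reasonable, not probable | Neither: 'Related' fails because another cause is reasonable, 'Not Related' fails because it is not probable | Can be met; no matching class |
| Probable | Not Related | Suspicion may still exist, as it needs no probability |

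The middle row is the gap.

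**Step 2. Do the thresholds agree?** In descending order of strictness, they are exclusion of every other reasonable cause (11.1.3), reasonable probability (SAR, 11.1.1) and suspicion (SUSAR, 11.1.1). A serious event in the middle row can satisfy the second and third tests and fail the first. The sections therefore contradict each other for the same event.

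**Step 3. What depends on the class?**

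| Procedure | Depends on 'Related'? |
|---|---|
| Recording of AEs on the CRF (11.1.4) | No; all are recorded regardless of attribution |
| General follow-up information on AEs (11.1.4) | No; given as necessary until resolved or stabilised |
| Explicit follow-up of related non-serious AEs (11.1.4) | Yes |
| SAE report to the Sponsor (11.1.5) | No; immediate for all |
| SUSAR report (11.1.6) | Same form and timing as an SAE; 11.1.3 is not cited, and the trigger is the definition in 11.1.1 |
| Relatedness item on the CRF (11.1.4), hence any relatedness detail in the AE and SAE listings (section 15) | Yes |

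**Step 4. Does the label matter for serious events?** Section 7.4 says that saliva collection has no known side effects. On that statement a serious event caused by the device would generally be unexpected, so the causality judgement would largely decide whether an SAE is also identified as a SUSAR. The Investigator's Brochure (HR-P-61) is not at hand and could qualify this.

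**The case against.** The strongest objection is that little in the protocol turns on the class. All SAEs reach the Sponsor at once, SUSARs travel on the same form at the same speed, SARs have no separate procedure, and the Chief Investigator reviews AEs as they are reported (11.1.7). The general follow-up sentence in 11.1.4 covers most of what the related-event rule adds. The CRF also asks for any other suspect drug or device. All of this stands, and it limits the point to labelling and to one follow-up rule. A reader might infer that possibly related events are not escalated; the documents do not support that.

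A reader might also infer that the wording would produce a false conclusion that the device is harmless. No such statement is planned; section 15 says only that AE and SAE details will be listed. Nor do the definitions send doubtful events to 'Not Related', because that class needs a probable other cause.

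It is tempting to illustrate the gap with sore gums or gagging during sampling and to attach a count. Read literally, the AE definition in 11.1.1 requires prolonged hospital care, permanent harm, lifesaving intervention or a contribution to death, so mild oral events might not qualify. However, 11.1.4 grades AEs from mild upwards and provides for non-serious ones. Sections 8.2 and 8.3 also keep out some women with competing oral causes or severe vomiting. The protocol gives no frequency for such events, so any count would only restate an assumption.

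Finally, the word 'reasonably' leaves room for judgement, and the SAE form (HR-P-60), which may offer other options, is not shown. Judgement may narrow the gap in practice, but it does not reconcile two sections that state different tests.

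**Conclusion.** The point holds in a limited form. The two classes in 11.1.3 are not exhaustive, and the test for 'Related' conflicts with the lower tests for SAR and SUSAR in 11.1.1. Three consequences follow: unreliable relatedness entries on the CRF; serious events that may not be recognised as SARs or SUSARs, although they are still reported as SAEs; and non-serious events that may drop out of the explicit related-event follow-up rule in 11.1.4.

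The size cannot be given as a number. The conclusion rests on the wording alone and on reading 'reasonable' as a lower level of certainty than 'probable', which is how 11.1.3 itself sets them against each other. It is a modest defect that should be corrected because it concerns safety classification and is cheap to remove.

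**What to change.** Reconcile 11.1.1 and 11.1.3 so that one causality threshold is used throughout. One workable form is:

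- *Related*: there is a reasonable possibility that the device or the sampling procedure caused or contributed to the event, even if another cause is also possible.
- *Not Related*: there is no such reasonable possibility.

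Use the same phrase in the SAR and SUSAR definitions, and carry it to the SAE form (HR-P-60) and the relatedness item on the CRF (HR-P-55). Other thresholds could serve. The essentials are that one test is used everywhere and that the second class is the complement of the first, so that each event has exactly one class.

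The cost is a wording amendment to two sections and two forms. Slightly more events will be classed as related and followed up. Recording and SAE reporting do not change.

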11.1.4 Procedure for Reporting Adverse Events

All AEs occurring during the safety window for the trial as defined above that are observed by the Investigator or reported by the participant, will be recorded during visits on the participants electronic

health record as source data and recorded on the CRF for the purposes of the study, whether or not attributed to the Salurate device.

The following information will be recorded on the CRF: description, date of onset and end date, severity, assessment of relatedness to investigational product, other suspect drug or device and action taken. Follow-up information should be provided as necessary until the AE has resolved or stabilised.

The severity of events will be assessed on the following scale: 1 = mild, 2 = moderate, 3 = severe.

Non-serious AEs considered related to the study intervention as judged by the Principal or Chief Investigator or the Sponsor will be followed up until resolution, or the event is considered stable.

It will be left to the Investigator's clinical judgment to decide whether an AE is of sufficient severity to require the participant's removal from treatment. A participant may also voluntarily withdraw from treatment due to what they perceive as an intolerable AE. If either of these occurs, the participant will be thanked for their involvement and followed up by telephone until the AE is resolved or considered stable. All withdrawals must be recorded using document *HR-P-62 - Early Withdrawal Form*.

11.1.5 Procedure for Reporting Serious Adverse Events

All SAEs must be reported to the Sponsor using document *HR-P-60 - SAE Reporting Form* immediately upon the Site Study Team becoming aware of the event being defined as serious. An assessment of Expectedness will be made by the Principal or Chief Investigator at the point of reporting.

It will be left to the Investigator's clinical judgment to decide whether an AE is of sufficient severity to require the participant's removal from treatment. A participant may also voluntarily withdraw from treatment due to what they perceive as an intolerable AE. If either of these occurs, the participant will be thanked for their involvement and followed up by telephone until the AE is resolved or considered stable. All withdrawals must be recorded using document *HR-P-62 - Early Withdrawal Form*.

11.1.5.1 Exceptions for SAE reporting

Hospitalisation for a pre-existing condition, including elective procedures planned prior to study entry, which has not worsened, does not constitute a serious adverse event.

11.1.6 Procedure for Reporting SUSARs

In the unlikely event of a SUSAR occurring, it must be reported on document HR-P-60 - SAE Report Form to the Sponsor immediately on the Investigation Team becoming aware of the event being defined as serious. An assessment of Expectedness will be made by the Principal Investigator at the point of reporting.

It will be left to the Investigator's clinical judgment to decide whether the SUSAR is of sufficient severity to require the participant's removal from treatment. A participant may also voluntarily withdraw from treatment due to what they perceive as an intolerable serious adverse reaction. If either of these occurs, the participant will be thanked for their involvement and followed up by telephone until the AE is resolved or considered stable. All withdrawals must be recorded using document HR-P-62 - Early Withdrawal Form.

11.1.7 Clinical Responsibility

Overall clinical responsibility for all participants enrolled onto the study will lie with the Chief Investigator, professor [name], who will review AEs as they are reported and provide clinical guidance for participants' safety through involvement as their treating clinician and in the oversight committee.

[name] is the Director of Fetal Medicine at St George's Hospital since 1999. He has authored over 400 peer-reviewed publications in indexed journals. His major research interest is placental dysfunction leading to pre-eclampsia, fetal growth restriction and stillbirth. He has led on the implementation of algorithm-based screening at St Georges which has led to an 80% reduction in preterm pre-eclampsia and a 30% reduction in perinatal death.

12 DATA HANDLING AND RECORD KEEPING

The data controller will be nominated by the Sponsor at the beginning of the study. Data processing will be by employees of the Sponsor under the direction of the data controller. The data will be used only for the purposes indicated in the currently-proposed Study. All data collected for the study will be subject to the General Data Protection Regulation and Data Protection Act 2018. The data collected will be anonymised and stored securely by Morgan Innovation & Technology Ltd, the data controller for the Salurate Study, and by the St George's clinical research archive, for a maximum of 15 years. This is for the purpose for processing the data, protection of IP and to ensure regulatory and legal requirements are evidenced when obtaining approvals.

Hospital-based. For the following functions:

- 1. Signing and storage of Consent Forms
- 2. Registration of Participants
- 3. Generating Study IDs, linked to Participant's ID
- 4. Clinical event data

These can be executed as paper-based hard copy, with attendant lock-and-key storage of documents, or electronically, on a software module written for the purpose and residing on a hospital-based system, and password controlled by the Investigator. Access to the hospital site is tightly controlled.

Also executed at the Hospital site, by clinical staff under the direction of the investigator, will be the creation, and storage of CRFs.

Sponsor's data-centre. For the following functions:

- 1. Receipt of compressed image data;
- 2. Calculation of results from image data;
- 3. Validation and storage of results;
- 4. Receipt and storage of CRFs identified only by Participant Study ID;
- 5. Linkage of Prediction-results and CRFs by Participant Study ID;
- 6. Statistical analysis

Two sets of Participant data relate; the sequential results of weekly self-testing for uric acid by each Participant, and the CRF of selected data from the Participant clinical records. Both sets shall be stored in separate areas: The weekly uric acid data shall reside in a Cloud-based system under the control of the data controller in the United Kingdom. The CRF will be stored on physical Servers owned by the sponsor and under the control of the data controller in the United Kingdom.

Data Protection: Test Results

- Recruitment will be carried out by a qualified medical professional approved by the Investigator and trained in Good Clinical Practice and the obligations of Researchers towards protection of the rights of volunteer participants, including personal data protection.
- Candidate participants will be advised that they will be asked to provide and test saliva samples, and to agree to the results being matched with certain data from their clinical records. These requirements are noted in the Participant Information Sheet (Doc:HR-P-53), in the oral recruitment interview, and in the Consent Form (Doc: HR-P-51) which they will be asked to sign.
- Upon giving informed consent, the subject's Consent Form will be registered on the Participant Register by the recruiter and assigned an individual Participant Study ID. The Register file linking Subject's Identity with Participant Study ID, either hard-copy or electronic, will be held by the Investigator. Staff of the Sponsor shall have no access to this linkage.
- Upon testing her sample, the participant will use their smart-phone app take an image / photo of the test cartridge. This image will then be compressed along with a time / date stamp and Participant Study ID. The compressed data is then transmitted to the Sponsor-held algorithm.
- These functions will be encoded in an application developed for the purpose by the Salurate supplier (which, in the case of the Trial, will be the Sponsor). The participant associated with each result will be identified only by their Study ID. Data transmitted will be encrypted by the smart-phone's communication protocol(s).
- The algorithm will convert the image to a digital uric acid concentration value.
- Test results will be validated and stored on a Cloud-based database managed by the Sponsor. The security levels and physical redundancy back-up facilities of reputable Cloud-system suppliers are generally much more robust than could realistically be provided by a stand-alone system.
- It should be noted that the sequence of uric acid test results for a pseudonymised participant would be entirely meaningless to an unauthorised observer.

Data Protection: Clinical Data

- At registration of a participant the linkage of participant Identifiable Information to Participant Study ID will be known only to the recruiter, and will be stored securely by the Investigator, either in a hard-copy register under lock-and-key or electronically under password protection. On completion of the Trial the register of linkage of participant Identifiable Information to Participant Study ID will be destroyed.
- As set out above, the participant will be well informed prior to her consent of the intention to extract certain clinical information from the records of every participant, and record them in a CRF on conclusion of the pregnancy. It will be emphasised that the data extraction will be done by a medical professional, and that the participant whose data goes in the CRF will be identified only by Participant Study ID.
- The information to be included in the CRF will be the presence or absence of any of the targeted end-points related to HDP, as defined in this Protocol. These will simply be characterised to the subject as "information relating to the progress and outcome of her pregnancy", but the detailed end-points can be made known on request.
- The completed CRF, identified only by Participant Study ID, will be generated electronically by clinical staff directly into the Sponsor-held data-base, and matched by Participant Study ID with the test-results already on file for the subject holding that Participant Study ID.

At no point will persons other than the participants' clinicians be aware of the subject's ID, or of any clinical information other than that specified in the CRF. The CRF information for a participant pseudonymised by Study ID would be meaningless to an unauthorised observer.

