5 AIMS AND OBJECTIVES

5.1 Study Aim

To assess the efficacy of the Salurate pregnancy remote self-monitoring system in predicting the onset of HDP. By comparing the Salurate system with traditional diagnostic methods, this study aims to determine the sensitivity, specificity, positive predictive value (PPV), and negative predictive value (NPV) of Salurate in identifying pregnant women. Additionally, the study aims to evaluate the time-to-diagnosis using the Salurate system in comparison to conventional diagnostic approaches.

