5.2 Primary Objective

a) To test the hypothesis that the inclusion of the Salurate pregnancy remote self-monitoring system in a pregnant woman's care pathway would predict the subsequent development of HDP prior to is currently possible using traditional methods.

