All clinical primary and secondary outcomes (maternal and neonatal) will be presented across the whole cohort as percentages with 95% confidence intervals, missing outcomes data will be presented. Women's characteristics at enrolment into the study will also be presented with percentages or summary statistics as appropriate. Salivary uric acid concentration (Salurate) observations will be presented graphically over time from the initial 10-14 week pregnancy record through to the end of study participation i) for the whole cohort, ii) by primary outcome (HDP present or absent), iii) for each secondary outcome, including adverse maternal or perinatal outcomes.

Numbers and percentages of missing Salurate reports will be presented by week of pregnancy with the number of women participating in the study as the denominator (which may vary in the last weeks of the study depending on when they give birth). This will be used to assess the degree of compliance of women to the testing regime. No multiple imputation or other forms of missing data replacement will be used to estimate missing values of Salurate. No missing data replacement will be employed for clinical outcomes or participant's characteristics at enrolment, and every effort will be made to record these data. We anticipate that rates of data missingness will be low.

Multilevel Logistic/Linear regression models, as appropriate, will be used to determine the relationship between Salurate results and the primary and secondary outcomes in this cohort. The Salurate algorithm will be employed and its sensitivity, specificity, positive predictive value (PPV) and negative predictive value (NPV) to identify the primary outcome will be presented with 95% confidence intervals. We will also determine how soon the primary outcome would be indicated using Salurate results and compare this with traditional prediction methods using standard NHS monitoring data.Subgroup analyses will explore whether the Salurate algorithm has greater diagnostic value in particular women according to baseline characteristics, although these analyses may not have enough statistical power to be definitive. Adverse Event and Serious Adverse Events details will be listed.

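### The outcome data listed in the protocol carry no date of HDP diagnosis or of first conventional detection, so the planned timing comparison cannot be computed from them

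*Protocol*

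**What the plan says.** Three places make timing part of what the study must show.

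- Section 5.1 gives the accuracy measures and then adds: "Additionally, the study aims to evaluate the time-to-diagnosis using the Salurate system in comparison to conventional diagnostic approaches".
- Section 5.2 states the primary hypothesis, that Salurate "would predict the subsequent development of HDP prior to is currently possible using traditional methods".
- Section 15 plans to determine how soon Salurate would indicate the primary outcome and to "compare this with traditional prediction methods using standard NHS monitoring data".

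The data rules are in Section 12, under the clinical data part. Clinical information is taken from the records, and staff will "record them in a CRF on conclusion of the pregnancy". Its content is described thus: "The information to be included in the CRF will be the presence or absence of any of the targeted end-points related to HDP". Nobody other than the participant's clinicians is to know her identity "or of any clinical information other than that specified in the CRF". Section 12 recognises two sets of participant data, the weekly uric acid results and the CRF. It ends the link to identity as follows: "On completion of the Trial the register of linkage of participant Identifiable Information to Participant Study ID will be destroyed".

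**The concern.** A comparison of when two methods detect a condition needs two dates per case: the first Salurate flag, and the first detection by routine care. The Salurate side is dated, because each weekly image carries a time and date stamp (Section 12). The clinical side, as listed, is not.

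The primary hypothesis concerns HDP that develops after the prediction. Sampling runs to the end of pregnancy (Section 10.5), so a woman can be flagged after her diagnosis. Without a diagnosis date that flag counts as a success in the same way as a true advance warning. The study summary in Section 3 claims an advantage of several weeks, and the listed data cannot show or refute it.

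**Working it through.** **1. The plan's own figures.** Section 15 gives figures for sensitivity only and none for timing.

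- Events: 4,000 × 0.115 = 460 (PE, PIH and IUGR together); 4,000 × 0.025 = 100 (IUGR).
- 95% half-width = 1.96 × √(p(1 − p)/n).
- n = 100: 9.8 points at p = 0.5 and 5.9 at p = 0.9 (stated: 10 and 6).
- n = 460: 4.6 points at p = 0.5 and 2.7 at p = 0.9 (stated: 5 and 3).

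These figures reproduce. None of them uses a diagnosis date, so they neither support the timing analysis nor suffer from the gap.

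**2. Which listed items could supply the clinical date?**

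- Section 10.4: baseline items at the dating scan, several with the date taken, plus the estimated due date. All precede HDP.
- Section 10.6: clinical diagnoses up to 6 weeks after pregnancy. No date or gestation of diagnosis is named.
- Section 10.7.4: blood pressure, urine, blood, symptom and fetal criteria. No dates are named.
- Section 11.1.4: onset and end dates of adverse events. The adverse event definition in 11.1.1 excludes outcomes caused by underlying disease. Serious event reports might date some HDP admissions, but not all cases.
- Section 15: routine NHS monitoring data are named as the comparator. No route into the dataset is given, and Section 12 allows none outside the CRF.
- The note in Section 5.3 defines current care by blood pressure, proteinuria, blood tests and PlGF. No serial or dated values of these are listed.

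**3. What presence or absence alone says about lead time.** Let lead time = diagnosis week − first flag week. Sections 10.6.1 and 10.6.2 place onset after 20 weeks, and Section 10.6 collects diagnoses to 6 weeks after pregnancy. For delivery at week D (an assumption), diagnosis lies between 20 and D + 6, a window of D + 6 − 20 weeks:

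| Assumed D | Window (weeks) | Lead time, flag at week 24 | Lead time, flag at week 30 |
|---|---|---|---|
| 34 | 20 | -4 to +16 | -10 to +10 |
| 37 | 23 | -4 to +19 | -10 to +13 |
| 40 | 26 | -4 to +22 | -10 to +16 |
| 42 | 28 | -4 to +24 | -10 to +18 |

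For any flag after week 20 shown here, even the sign is open. For a flag at week 16 and D = 40 the sign is known, but the size runs from +4 to +30 weeks.

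**The case against.** The strongest reply is that the Section 12 sentence is a data protection statement and not a full CRF specification, and that the CRF (HR-P-55) is not at hand. Both points stand. A reader might infer that the CRF holds nothing but presence or absence. The documents do not support that: Sections 10.4, 10.6 and 11.1.4 put other items on it, some of them dated. Nor can one say that the comparison is impossible in fact, because HR-P-55 may have date fields and Section 15 shows that NHS monitoring data are meant to be used. What remains is that no listed item is an HDP diagnosis date, although the protocol does name dates for other items.

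A reader might also infer that destroying the register blocks recovery of the dates. During the study it does not. Sites are queried about missing data (13.4), 10% of CRFs are checked monthly against patient records (13.2), and the study ends only at 4,000 complete datasets (14). The risk is confined to queries that arise after completion.

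Two smaller points also stand. Time-to-diagnosis is an added part of the aim in 5.1, while the primary objective in 5.2 is earlier prediction; the two need the same dates but are not the same statement. Delivery timing must be obtained in some form, since birth weight for gestational age (10.7.1) needs it, but it is not itemised.

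The analysis plan is not a full answer. It can define lead time, but it cannot supply dates that were not collected.

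**Conclusion.** The point holds as an inconsistency between a stated data rule and the study's main question. From the data the protocol lists, lead time cannot be computed, and flags before diagnosis cannot be separated from flags after it. With delivery assumed at week 40, the range of possible lead times for a single case is 26 weeks wide. The accuracy measures against eventual HDP are still computable, but without dates they do not show that the flag came first.

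The conclusion rests on the protocol text alone, and an adequate HR-P-55 would reduce it to a correction of wording. The bounds rest on the assumed delivery weeks and on the 20-week onset in 10.6.1 and 10.6.2; Section 10.6.3 sets no such start for every case of superimposed pre-eclampsia. No count of affected women is given, because the 460 in Section 15 mixes HDP with IUGR and the overlap is not stated.

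**What to change.** 1. Amend the Section 12 sentence on CRF content so that it agrees with Sections 10.4, 10.6, 11.1.4 and 15.
2. List as CRF items: the date and gestation of first HDP diagnosis; the date of first conventional indication (first qualifying blood pressure, urine or blood result, and PlGF where done); and the date of delivery. Check HR-P-55 against this list.
3. State how routine NHS monitoring data enter the dataset, given the limit in Section 12 on what leaves the clinicians.
4. Keep the linkage register until data queries are closed.

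The definition of lead time, including how unflagged cases are handled, can be left to the analysis plan.

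The cost is some added abstraction time per case, from records that staff are already reading. No sample size figure changes.
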